## **Participant Groups**

Participants will be randomly assigned *a priori* to either the Experimental group (auditory training) or Control group (no auditory training) using simple random assignment. Because the third group (Speech Group) is added after the experimental and control groups have completed their participation, to provide additional power to the regression analysis, the Speech group will be assigned by the investigator. Because this study will detect whether or not significant changes in MOC activity and speech perception across time occurred as a result of auditory training, the Control group is needed to establish the test-retest reliability of our outcome measures in the absence of any training. Participants will be informed of which group they are assigned to at the initial visit, but they will not be allowed to change groups.

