## **Sample Size**

Based on power analyses, the study will require participation of at least 12 participants in the experimental group. Sample sizes were estimated using data from studies that reported differences in MOC activity or speech perception before and after an auditory training program. Pre- and post-training means and standard deviations were used to compute the minimum sample sizes ( $n$ ) needed to detect a mean difference in paired samples (i.e., mean results for pre- versus post-training performance in the same participants), using methods described in Dupont and Plummer (1990, *Control Clin Trials*, 11:116-128). Sample sizes were calculated using a type I error rate of 0.05 and 80% power to detect differences in mean performance between pre-training and post-training. For MOC activity, the results of de Boer and Thornton (2008, *J Neurosci*, 28:4929-4937) indicated a minimum of  $n = 10$ . For word recognition, the results of Henshaw and Ferguson (2014, *Proc ISAAR 2013*) indicated a minimum of  $n = 12$ . For sentence recognition, the results of Song et al. (2011, *Cereb Cortex*, 22:1180-1190) indicated a minimum of  $n = 11$ . An

equal number of participants will be assigned to the control group. To account for possible subject attrition, we tentatively plan to recruit up to 40 total participants (20 each in the Experimental and Control groups).

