### **Study Timeline**

The experiment will be carried out over the course of 3 years. Disbursement of research funds from NIH is expected to occur on or before 12/1/2015. Participant recruitment and data collection will begin immediately after disbursement of funds. Using a conservative estimate of recruiting one new participant per week, it will take 40 weeks to recruit all 40 participants. The last participant will therefore be tested approximately 15 weeks from that point, for a total of 55 weeks to complete data collection. We will allot an additional 12 months for data collection to account for potential delays in participant recruitment and attrition.

This study consists of one experiment that will last 3 years total. Each participant is expected to complete all study procedures in from 1 to 14 study visits, ideally over a 10-week period. However, we will allow for the visits to take place across a one year period to account for participants needing to miss or reschedule some visits. Additionally, we will allow each subject to make-up a maximum of 2 study visits. All study visits will last between 2-3 hours. Thus, the maximum amount of participation for each participant is 42 hours during a maximum one year window for data collection.

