All participants will undergo otoscopy, immittance testing, TEOAE testing, word testing, and sentence testing at each visit. Participants in the experimental group will also complete the auditory training program, with baseline (pre-training) measures at visit 1, training occurring in visits 2-11, and visit 12 serving as the retention (post-training) measurements. These participants will therefore undergo a total of 15 hours of auditory training spread across 10 visits, plus pre- and post-tests. Pure-tone audiometry will be repeated for all participants at visits 6, 11, and 12 to detect any significant changes in hearing thresholds during the course of a participant's participation (not due to actual participation in the study because all sound levels will be presented at safe volumes). Such changes in audiometric measures are not likely to occur over this relatively short time period. All participants (except those in the Speech group) will be asked to return for a visit twice a week for the first 6 weeks (visits 1-11) and return for the final visit 4 weeks later (visit 12). Each subject will be allowed a maximum of two make-up visits in case a visit needs to be stopped early, resulting in a maximum of 14 study visits.

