### **Data Analysis**

Correlational analyses will be used to determine the correspondence between changes in MOC activity and changes in speech perception during the course of auditory training. Statistical analyses of test-retest reliability from the Control group data will be used to determine what constitutes a statistically significant change in MOC activity and speech perception ability. Repeated measures analyses of variance (both within a study visit and across study visits) will also be performed.

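### Attrition is expected and outcomes are tested at every visit, but the across-visit repeated-measures ANOVA has no rule for people who leave before visit 12

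*Combined protocol and SAP*

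**What the plan says.** The Sample Size section powers a paired comparison, "mean results for pre- versus post-training performance in the same participants", and arrives at a minimum of 12 in the Experimental group. It then allows for loss: "To account for possible subject attrition, we tentatively plan to recruit up to 40 total participants (20 each in the Experimental and Control groups". The Study Timeline section adds 12 months of data collection "to account for potential delays in participant recruitment and attrition".

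Under Order of Procedures, outcomes are collected throughout: "All participants will undergo otoscopy, immittance testing, TEOAE testing, word testing, and sentence testing at each visit". Training runs over visits 2 to 11, with "visit 12 serving as the retention (post-training) measurements" four weeks after visit 11. Up to two make-up visits are allowed, within a one-year window.

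The Data Analysis section has three sentences: correlations between changes in MOC activity and in speech perception, change thresholds taken from Control test-retest data, and then "Repeated measures analyses of variance (both within a study visit and across study visits) will also be performed". It gives no list of visits, no analysis population and no rule for incomplete series.

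**The concern.** A standard repeated-measures ANOVA needs a value at every level of the within-person factor. Whether the levels are all 12 visits or only visits 1 and 12, a person without visit 12 is excluded, although their earlier visits were tested. Recruiting 20 to secure 12 protects the headcount but does not say who is analysed.

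The quantity at risk is the within-arm change. Randomisation does not protect it, because it compares people with themselves and the people who stay may differ from those who leave. The between-arm comparison is distorted mainly if leaving differs by arm, which is possible because only one arm trains. Without a stated rule, the choice between completers and all available data can be made after the results are seen.

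The concern is permanent dropout. Make-up visits cover most sporadic misses: if each visit were missed with probability 5% (an assumption), 20 × P(Bin(12, 0.05) ≤ 2) = 19.6 of 20 would still complete.

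**Working it through.** **1. The plan's own figure.** The minimum of 12 cannot be rebuilt forward, because no mean change or SD is given. Solved backward (paired t-test, 80% power, 0.05 taken as two-sided), 12 people can detect a change of 0.889 SD. Going from 12 to 20 allows for 40% loss: 12 / (1 − 0.40) = 20. At 0.889 SD, power is 96.5% with 20 completers, 91% with 16 and 80% with 12. The sample size therefore survives the loss it allows for.

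**2. Data discarded.** Assume leavers stop after visit 6 and all 12 visits enter.
- 4 of 20 leave: 4 × 6 = 24 of 24 + 16 × 12 = 216 person-visits are dropped (11%).
- 8 of 20 leave: 8 × 6 = 48 of 48 + 12 × 12 = 192 are dropped (25%).

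**3. Bias in the completers' within-arm change.** Assumptions, none from the documents: 20 per arm, correlation 0.7 between any two visits, no true change, and the lowest scorers on some quantity leave after visit 6. With unit variance at each visit, the person variance is 0.7 and the visit variance 0.3, so the SD of change is √0.6. In SD of change,

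bias = link × corr(quantity, change) × m,

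where m is the mean standardised score of those kept (0.333 with 16 of 20, 0.618 with 12), and the link is the correlation between the score that decides leaving and the quantity.
- Progress (visit 6 minus visit 1): corr = 0.3/0.6 = 0.5.
- Baseline: corr = −0.3/√0.6 = −0.387.
- Visit-6 level: corr = 0.

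The formula gives 0.5 × 0.333 = +0.167 and −0.387 × 0.333 = −0.129 with 16 kept. With 12 kept it gives +0.309 and −0.239. Simulation (20,000 runs) agrees:

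| Completers, within arm | 16 kept: bias / error | 12 kept: bias / error |
|---|---|---|
| Random leaving | 0.00 / 5.1% | 0.00 / 5.0% |
| Low visit-6 level | 0.00 / 5.0% | 0.00 / 5.0% |
| Low baseline, perfect link | −0.131 / 8.4% | −0.240 / 12.8% |
| Low progress, link 0.5 | +0.083 / 6.2% | +0.156 / 8.0% |
| Low progress, perfect link | +0.167 / 10.9% | +0.310 / 18.6% |

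The perfect-link figure at 16 kept rises if people differ in true slope. It is 11.8% when half the change variance is true slope. It is about 14% when three quarters is: slope variance 0.9 and visit variance 0.15, visit 6 at week 2.5 of 9, so corr = (0.278 × 0.9 + 0.15) / √(0.369 × 1.2) = 0.60 and bias = 0.60 × 0.333 = +0.20.

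**4. Between arms, completers.** With the same leaving rule in both arms, bias is within 0.01 SD and error is 4.9% to 6.0%. If Experimental leavers are those with low progress and Control loses people at random, bias with 16 kept is +0.169 SD and error 7.9%.

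**5. A mixed model on all collected visits.** With equal variances in the two arms, a model with visit, group, visit-by-group and a person intercept and slope gave bias within 0.03 SD and error of about 3% to 5.5% whenever leaving depended on recorded values. A single covariance for both arms is not safe. When the Experimental arm's change variance was twice Control's, it gave 7.5% to 8.5% within-Experimental error, and 10% with progress-related leaving. Arm-specific covariances gave about 5%, with bias near 0.01 SD against about +0.2 SD for completers.

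**The case against.** Exclusion is inferred. The plan does not list the visits or say how the ANOVA is fitted. Some software fits the same model by likelihood, and an ANOVA over visits 1 to 11 would keep someone lost only in the final four-week gap. That stands, and it is why the point is conditional on visit 12 being a level. Including it is the natural reading, since it is the post-training measurement.

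The ANOVA is named last, after the correlations and the Control-based thresholds. That also stands, but it is the only named analysis that tests mean change across visits, which is what the Sample Size section powers. The correlations face the same incomplete series and need a rule too.

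The harm may be small. Nothing in the documents ties leaving to progress, and participants are paid after every visit. Random loss gives no bias. This limits the severity.

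A mixed model can bring its own error. Pooling variances over arms is unsafe if training makes change more variable, which is plausible because the Synopsis reports that earlier training strengthened MOC function only in some participants. This is right for a pooled model, and arm-specific variances repair it.

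A reader might infer that the trial will overstate the benefit of training. The documents do not support that: they give no rate or mechanism, and the bias can be zero or go in either direction.

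**Conclusion.** The gap is real: attrition is foreseen, the data that would inform its handling are collected, and no rule is stated. On the natural reading, a standard ANOVA analyses completers only. With 16 of 20 kept, within-arm error is 5% under random loss, about 6% with a link of 0.5 to progress, and about 11% to 14% with a perfect link. The range rests on the assumed retention, correlation and leaving rule.

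Two stronger readings fail. The sample size is not wrong, since 20 per group still leaves 12 at 40% loss. Nor is the randomised comparison generally invalid, since it is largely protected when both arms lose people alike. The severity is minor to moderate.

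**What to change.** In the Data Analysis section, replace the across-visit ANOVA with a linear mixed model in the randomised Experimental and Control groups only. The Speech group stays out because "the Speech group will be assigned by the investigator".
- Data: every collected visit from everyone with a baseline.
- Fixed effects: visit (categorical), group, visit-by-group.
- Random effects: person intercept and slope on weeks since visit 1, because visit 12 comes after a longer gap.
- Random-effect and residual variances separate by arm, or the Experimental arm fitted alone for the within-arm contrast.
- Degrees of freedom: Kenward-Roger or Satterthwaite.
- Report: visit 12 minus visit 1 within the Experimental group and between groups, completers as a sensitivity analysis, and losses by group.

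State a separate rule for incomplete series in the correlations. If the randomised groups are still being tested, invite Experimental participants who stop training without withdrawing consent to the scheduled visit 12. Participant Groups has the Speech group added after the other two have finished, so this may come too late. Some would not return in any case.

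The analysis change costs a few sentences and no new data. It has limits. The model assumes leaving depends on recorded values. If leaving follows a person's unrecorded true slope, it removes little: +0.19 SD against +0.23 for completers with 16 kept. Arm-specific variances also give up the power gained by pooling, which was part of the rise from 92.2% to 95.0% within arm with 16 kept. Between arms even the pooled model gains little (69.5% to 70.0%), so the case for the change is bias and a rule fixed in advance, not power.
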